APPENDIX I. HEART FUNCTION BY NEW YORK HEART ASSOCIATION (NYHA) CLASSIFICATION

Class	Patient Symptoms
I	No limitation of physical activity. Ordinary physical activity does not cause undue fatigue, palpitation, dyspnea (shortness of breath). Patient has no symptoms when walking, climbing stairs, etc.
п	Slight limitation of physical activity. Comfortable at rest. Ordinary physical activity results in fatigue, palpitation, dyspnea (shortness of breath) or angina.
ш	Marked limitation of physical activity. Comfortable at rest. Less than ordinary activity (e.g. walking short distance 20-100m) causes fatigue, palpitation, dyspnea or angina.
IV	Unable to carry on any physical activity without discomfort. Symptoms of heart failure at rest. If any physical activity is undertaken, discomfort increases.

APPENDIX II. GUIDANCE REGARDING POTENTIAL INTERACTIONS WITH CONCOMITANT MEDICATIONS

The use of any natural/herbal products or other "folk remedies" (e.g. Ginseng and other Traditional Chinese Medicine) should be discouraged, but use of these products, as well as use of all vitamins, nutritional supplements, and all other concomitant medications must be recorded in the eCRF.

AZD4205 is an investigational drug for which no data on *in vivo* interactions are currently available in human. Based on *in vitro* data and predicted clinical exposure data, AZD4205 is considered unlikely to cause clinically significant drug interactions through inhibition or induction of cytochrome P450 enzyme activity.

In vitro data have shown that the principal CYP enzymes responsible for the Phase I metabolism of AZD4205 is CYP 3A4. Therefore, drugs strongly inhibiting CYP3A4/5 metabolism are recommended not to combine with AZD4205. Drugs inducing CYP3A4/5 metabolism should also be avoided to combine with AZD4205 if possible.

During the treatment of AZD4205, live vaccines should be avoided.

Drugs inhibiting CYP3A4/5 metabolism that Sponsor recommend are not combined with AZD4205.

The contribution of Phase I metabolism to the total clearance of AZD4205 is currently unknown but, to ensure patient safety, the following potent inhibitors of CYP3A4/5 must not be used during this study for any patient receiving AZD4205.

Table A1. Drug inhibiting CYP3A4/5

Contraindicated drugs	Withdrawal period prior to AZD4205 start
Ketoconazole, itraconazole, indinavir, saquinovir, nelfinavir, atazanavir, amprenavir, fosamprenavir, troleandomycin, telithromycin, fluconazole, nefazodone, cimetidine, aprepitant, miconazole, fluvoxamine	1 week
Amiodarone	27 weeks
Erythromycin, clarithromycin, verapamil, ritonavir, diltiazem	2 weeks

This list is not intended to be exhaustive, and a similar restriction will apply to other agents that are known to strongly modulate CYP3A4/5 activity. Appropriate medical judgment is required. Please contact Sponsor with any queries you have on this issue.

Patients should abstain from eating large amounts of grapefruit and Seville oranges (and other products containing these fruits, e.g., grapefruit juice or marmalade) during the study because of inhibition of intestinal CYP3A4 metabolism, e.g. no more than a small glass of grapefruit juice (120 mL) or half a grapefruit or 1 to 2 teaspoons (15 g) of Seville orange marmalade daily.

Drugs inducing CYP3A4 metabolism that Sponsor recommend are not combined with AZD4205

To avoid potential reductions in exposure due to drug interactions, the following CYP3A4/5 inducers should be avoided if possible.

Table A2. Drug inducing CYP3A4/5

Contraindicated drugs	Withdrawal period prior to AZD4205 start
Phenytoin, rifampicin, St. John's Wort, carbamazepine, primidone, griseofulvin, barbiturates, troglitazone, pioglitazone, oxcarbazepine, nevirapine, efavirenz, rifabutin	3 weeks
Phenobarbitone	5 weeks

This list is not intended to be exhaustive, and a similar restriction will apply to other agents that are known to strongly modulate CYP3A4/5 activity. Appropriate medical judgment is required. Please contact Sponsor with any queries you have on this issue.

Additional guidance for drugs whose exposure may be affected by AZD4205

In vitro data suggests that AZD4205 has weak inhibition on the drug transporters including P-gp, OAT1 and OAT3 (IC₅₀ >100 μM), and moderate inhibition on BCRP, OATP1B1, OCT2, MATE1 and MATE2-K (IC₅₀s of 37.1, 47.4, 10.2, 0.725 and 0.739 μM, respectively). Exposure of those co-medications whose disposition depends on kidney OCT2, MATE1 and MATE2-K could be altered. DDI risk via inhibition of intestinal CYP3A4 metabolism and BCRP efflux and hepatic OATP1B1 uptake could not be ruled out. Thus, co-medication whose disposition/elimination mainly depends on these transporters with narrow therapeutic index and drug related safety events should be closely monitored following the recommendation from drug label.

Table A3. Exposure, pharmacological action and toxicity that may be increased by AZD4205

	Warning of possible interaction and corresponding advices
Rosuvastatin Pravastatin Pitavstatin Atorvastatin Simvastatin Fluvastatin	These drugs are permitted but caution should be exercised. It is recommended that the starting and maintenance dose should be as low as possible and should be guided by the drug label. In addition, the times of administration of the statins and/or ezetimibe and AZD4205 should be staggered such that the maximum levels of both drugs in the gut do not coincide. For patients receiving these drugs, additional monitoring of low-density lipoprotein (LDL) cholesterol levels and liver enzymes is advised. If the patient experiences any potentially relevant adverse events suggestive of muscle toxicity including unexplained muscle pain, tenderness, or weakness, particularly if accompanied by malaise or fever, the lipid-lowering treatment should be stopped and creatine kinase (CK) levels should be checked, and any appropriate further management should be taken.
Metformin	Active secretion via kidney transporters are highly involved for metformin elimination, thus inhibition of these transporters has the potential to interfere with the transport of metformin and ultimately affect both plasma and intracellular concentrations of metformin. Lactic acidosis, a rare but serious complication, can occur due to metformin accumulation. Thus, metformin is permitted with cautions. Please follow the recommendation stated in metformin label. If patients experience any potentially relevant adverse events as metformin label, metformin associated lactic acidosis tests should be check and metformin treatment should be stopped to follow metformin drug label.

Drugs that may prolong QT interval

The drugs listed in this section are taken from information provided by The Arizona Center for Education and Research on Therapeutics and The Critical Path Institute, Tucson, Arizona and Rockville, Maryland. Ref: http://www.arizonacert.org/medical-pros/drug-lists/druglists.htm.

Drugs known to prolong QT interval

The following drugs are known to prolong QT interval or induce Torsades de Pointes and should not be combined with AZD4205. Recommended withdrawal periods following cessation of treatment with these agents are provided in the table below

Table A4. Drugs prolonging QT interval

Contraindicated drug	Withdrawal period prior to AZD4205 start
Clarithromycin, droperidol, erythromycin, procainamide	2 days

Cisapride, disopyramide, dofetilide, domperidone, ibutilide, quinidine, sotalol, sparfloxacin, thioridazine	7 days
Bepridil, chlorpromazine, halofantrine, haloperidol, mesoridazine	14 days
Levomethadyl, methadone, pimozide	4 weeks
Arsenic trioxide	6 weeks*
Pentamidine	8 weeks
Amiodarone, chloroquine	1 year

^{*} Estimated value as PK of arsenic trioxide has not been studied

Drugs that may possibly prolong QT interval

The use of the following drugs is permitted (notwithstanding other exclusions and restrictions) provided the patient has been stable on therapy for the periods indicated.

Table A5. Drugs that may possibly prolong QT interval

Contraindicated drug	On treatment duration prior to AZD4205 start
Alfuzosin, chloral hydrate, ciprofloxacin, dolasetron, foscarnet, galantamine, gemifloxacin, isridipine, ketoconazole, levofloxacin, mexiletine, nicardipine, octreotide, ofloxacin, ondansetron, quetiapine, ranolazine, telithromycin, tizanidine, vardenafil, venlafaxine, ziprasidone	2 days
Amantadine, amitriptyline, amoxapine, clozapine, doxepin, felbamate, flecainide, fluconazole, fosphenytoin, gatifloxacin, granisetron, imipramine, indapamide, lithium, moexipril/HCTZ, moxifloxacin, risperidone, roxithromycin, sertraline, trimethoprin-sulfa, trimipramine, voriconazole	7 days
Azithromycin, citalopram, clomipramine, itraconazole, nortriptyline, paroxetine, solifenacin, tacrolimus	14 days
Fluoxetine	5 weeks
Protriptyline	6 weeks
Tamoxifen	8 weeks

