- 4. Patients with severely decreased lung function (i.e. any parameter of FEV1, and DLCO < 60% of predicted value). Past medical history of pneumonitis, drug-induced interstitial lung disease, radiation pneumonitis which required steroid treatment, or any evidence of clinically active interstitial lung disease.
- 5. Patients with disease condition which requires the treatment of immunosuppressants, biologics, or NSAIDs (non-steroid anti-inflammatory drugs).
- 6. Active infections including:

- History of known latent or active tuberculosis (TB), e.g. signs of active or latent TB on PPD test or chest X-ray/CT, skin test showing an induration of >10 mm or more, or positive results of screening tests according to local recommendations.
- Known infection with human immunodeficiency virus (HIV), or serologic status reflecting active hepatitis B or hepatitis C infection as follows:

	Inclusion	Exclusion
HIV antibody	Negative	Positive
HCV antibody	Negative	Positive
HBV	Both HBsAg and HBcAb are negative	Either HBsAg or HBcAb is positive

- Active viral infections (i.e. zoster) other than hepatitis B or C.
- Infections requiring oral or intravenous antimicrobial therapy or interferon.
- Bacterial infections including pneumonia within 30 days.
- 7. Any of the following cardiac criteria:
 - Congestive heart failure (CHF) per New York Heart Association (NYHA) classification > Class II (see Appendix I).
 - Clinically significant valvular diseases, hypertrophic or constrictive cardiomyopathy.
 - Any clinically significant abnormalities in rhythm, conduction or morphology of resting ECG, e.g., complete left bundle branch block, third degree heart block, and second-degree heart block, PR interval > 250 msec.
 - Cardiac ventricular arrhythmias requiring anti-arrhythmic therapy.
 - Acute Myocardial Infarction (AMI) within 6 months prior to starting treatment, unstable angina or new-onset angina.
 - Patients with heart transplant.
 - Mean resting corrected QTcF interval (QT_C) > 450 ms on screening triplicate electrocardiogram (ECG).
 - Patients with factors that increase the risk of QT prolongation or arrhythmic events (e.g., heart failure, hypokalaemia, congenital long QT syndrome, any concomitant medication known to prolong the QT interval (Appendix II)) or family history of long QT interval syndrome or unexplained sudden death under 40 years of age in first degree relatives).

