4.3.2 Supportive care and prophylactical therapy

Patients may receive any medication that is clinically indicated for treatment of adverse events, unless specifically excluded. All concomitant medications should be captured on the electronic CRF (eCRF).

- 1. Other anticancer agents, investigational agents and radiotherapy should not be given while the patient is receiving study treatment. The patient may be allowed to take localized palliative radiotherapy for pain control if it has been confirmed that there is no disease progression on the local lesion.
- 2. Blood transfusions are allowed at any time during the study treatment phase.
- 3. Granulocyte colony stimulating factors should not be used prophylactically during Cycle 1. Use of prophylactic colony stimulating factors may be considered after Cycle 1 following discussion with the Sponsor Study Physician.
- 4. Supportive care and other medications that are considered necessary for the patient's well-being, may be given at the discretion of the investigator.
- 5. Serious infection is an identified risk for the approved JAK inhibitors, and patients with relapsed or refractory PTCL are at a high risk of opportunistic infection. Pneumocystis pneumonia has been reported in the clinical study with AZD4205. Therefore, **for all patients during the treatment, pneumocystis prophylaxis is required**. Please follow institutional guidelines or European Conference on Infections in Leukemia (ECIL) guideline (Maertens J et al. 2016, Cordonnier C et al. 2016).
- 6. For patients with history of cytomegalovirus (CMV) infection that required treatment, prophylactic treatment and monitoring for reactivation via serology or viral load detection per institutional guidelines is recommended.
- 7. For patients with tumor response during the study, it is not recommended to subsequently receive bone marrow transplantation, e.g. autologous or allogenic stem cell transplantation (SCT). If patients require SCT, AZD4205 should be discontinued

after discussion with sponsor study physician, and tumor response assessment should still be performed as scheduled after discontinuation.

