5.2.2 Potential risks

Non-clinical toxicity studies of AZD4205 in rats and dogs and safety pharmacology experiments have been summarized in Section 2.3 of this protocol, which may indicate the potential adverse effects of AZD4205 in human. Further detailed information of non-clinical toxicity findings is available in the Investigator Brochure. The monitoring and management of the potential adverse effects of using AZD4205 is discussed below.

Cardiovascular effects

Patients who have unstable cardiac conditions and risk factors for QT prolongations will be excluded from participation in this study (detailed exclusion criteria are listed in Section 4.2). Concomitant use of regular medications that may prolong the QT interval will be restricted whenever feasible (See Appendix II), but patients may receive any medication that is clinically indicated for the treatment of AEs. Electrolyte and vital sign assessments, including pulse rate and blood pressure, will be monitored regularly throughout the study (See Section 6.1). Twelve lead ECG will be conducted throughout the study to monitor any

change of QT interval. Confirmed QTc prolongation (> 500 msec absolute or > 60 msec above baseline) is the dose interruption criteria (See Section 6.4.3). The investigator or designated physician will review each ECG prior to discharge from the clinic and may refer to a local cardiologist if appropriate for immediate management of the patients. A paper copy should be filed in the patient's medical records. If an abnormal ECG finding at screening or baseline is considered to be clinically significant by the investigator, it should be reported as a concurrent condition. An Echocardiogram or MUGA scan to assess LVEF will be performed at screening prior to first dose of AZD4205 to evaluate any pre-existing cardiac abnormality, followed by Cycle 3 Day 1, and then every 12 weeks, and wherever and whenever necessary as clinically indicated throughout the study. An asymptomatic LVEF decrease to < 40% or LVEF [40-54%] and LVEF decrease ≥ 10% from baseline or any symptomatic LVEF decrease are the dose interruption criteria (See Section 6.4.5 and Appendix VII). Both high sensitive troponin T testing and NT-pro BNP will be performed at screening, baseline and each subsequent cycle.

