conditions. It's known that heavily treated patients with hematological malignancies are at a high risk of PCP infection, and many approved JAK inhibitors also observed PCP infection. Hence, adequate prophylaxis is critical in high-risk conditions (Cordonnier C et al. 2016). Most cases of PCP occur from reactivation of latent infection, although cases of person-to-person transmission have been reported. In a Cochrane meta-analysis (including 1155 adult patients with acute leukemia and recipients of an HSCT and solid organ transplant), the incidence of PCP was reduced by 91% [relative risk (RR) 0.09] with prophylaxis compared with placebo, no treatment or treatment with antimicrobial agents showing no activity against P. jirovecii (e.g. quinolones) (Green H et al. 2007). Pneumocystis pneumonia has been reported in the clinical study with AZD4205. Therefore, for all patients during the treatment, pneumocystis prophylaxis is required. Please follow institutional guidelines or refer to below guidance (Maertens J et al. 2016, L. Cooley et al. 2014).

Trimethoprim/sulfamethoxazole (TMP/SMZ) is the preferred drug for the primary prophylaxis of Pneumocystis infections in adults. The recommended dose is either a single-strength (80/400 mg) tablet daily or a double-strength tablet (160/800 mg) three times weekly. Limitations in TMP/SMX prophylaxis include documented hypersensitivity, renal impairment, myelosuppression and gastrointestinal disturbance. The true rate of adverse reactions is unknown, but in the adult HSCT population it is estimated to be in the range of 5–15%, and in children it is much lower (Souza JP et al.1999).

Second-line agents for PJP chemoprophylaxis may be given to the patients if TMP/SMZ is intolerant or contraindicated, including dapsone, atovaquone or pentamidine (see Table 17).

Table 17 Dosing schedule for PCP chemoprophylaxis for adult patients with hematological malignancies

	Dosing schedule		
	80 + 400 mg (one SS tablet) orally, daily		
TMP-SMZ	Or		
	160 + 800 mg (one DS tablet) orally, three times a week		
Dapsone	100 mg orally, daily		
Pentamidine	300 mg inhaled through nebuliser, every 4 weeks (administered through a jet- nebuliser producing a droplet size of 1–2 microns)		
Atovaquone	1500 mg orally, daily with a high-fat meal		

Monitoring and management of cytomegaloviral infections

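### Appendix II says not to combine pentamidine with AZD4205, while Appendix VII Table 17 offers it as prophylaxis during AZD4205; seven other drugs carry differing rules across Appendix II tables

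*Protocol*

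**What the plan says.** **Pentamidine.** Appendix II, on drugs known to prolong QT, opens Table A4 with: "The following drugs are known to prolong QT interval or induce Torsades de Pointes and should not be combined with AZD4205". The table lists pentamidine without a route and gives a withdrawal period of 8 weeks before AZD4205 starts. Exclusion criterion 7 in Section 4.2 refers to Appendix II for co-medication known to prolong QT.

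Section 4.3.2 item 5 states that "for all patients during the treatment, pneumocystis prophylaxis is required", and Section 5.2.2 and the footnote on AZD4205 administration in Table 3 say the same. Appendix VII, part 4, then says: "Second-line agents for PJP chemoprophylaxis may be given to the patients if TMP/SMZ is intolerant or contraindicated, including dapsone, atovaquone or pentamidine". Table 17 gives pentamidine as "300 mg inhaled through nebuliser, every 4 weeks".

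**Softening text.** Section 5.2.2 limits QT-prolonging co-medication only so far as feasible, refers to Appendix II, and continues: "but patients may receive any medication that is clinically indicated for the treatment of AEs". Section 4.3.2 item 4 adds: "Supportive care and other medications that are considered necessary for the patient's well-being, may be given at the discretion of the investigator".

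**Other drugs in Appendix II.** Table A1 bars its potent CYP3A4/5 inhibitors for any patient receiving AZD4205. Table A5 permits its drugs once the patient has been stable on them for a stated period, although its drug column is headed as a list of contraindicated drugs. Trimethoprim-sulfa, the preferred prophylaxis in Appendix VII, is in Table A5 with a 7-day period.

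**The concern.** A site that gives pentamidine under Table 17 does what Table A4 says should not be done. Another site that withholds it under Table A4 is also following written text. A monitor cannot tell from the protocol whether such use is compliant or a deviation. The same uncertainty applies to drugs that Table A1 bars and Table A5 permits.

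Second-line prophylaxis is foreseeable. Prophylaxis is mandatory, Appendix VII lists myelosuppression among the limitations of TMP/SMZ, and Section 5.2.3 lists neutropenia and thrombocytopenia among the most common drug-related events of grade 3 or higher. QT is also a recognised risk: Section 2.3.2 reports QT increases in dogs at all doses tested, and Table 1 requires permanent discontinuation for QTcF above 500 ms or more than 60 ms above baseline.

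What is at stake is consistent safety guidance for a required co-medication. The efficacy result is not at stake.

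**Working it through.** No figure in the plan needs reproducing. The check sets the passages side by side, then compares the Appendix II lists by printed drug name.

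**1. Table 17 agents against Appendix II**

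| Agent in Table 17 | Place in Appendix II | Rule there |
|---|---|---|
| TMP-SMZ | A5 | permitted if stable for 7 days before AZD4205 starts |
| Dapsone | none | no restriction listed |
| Pentamidine | A4 | not to be combined; 8 weeks' withdrawal |
| Atovaquone | none | no restriction listed |

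**2. Does any text reconcile pentamidine?**
- The Section 5.2.2 exception covers treatment of adverse events. Prophylaxis is not treatment of an adverse event.
- Section 4.3.2 item 4 gives general discretion and names neither pentamidine nor Table A4. The opening of that section allows medication for adverse events only where it is not specifically excluded.
- Table 17 specifies inhalation and Table A4 gives no route. An exemption for inhaled use may have been intended, but none is written.
- At entry, the A4 withdrawal period is 8 × 7 = 56 days against a 28-day screening window (Section 3.1.3). Table 17 would allow the same drug once treatment has begun.

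**3. Entries per table, summed over rows**
- A1: 16 + 1 + 5 = 22
- A2: 13 + 1 = 14
- A4: 4 + 9 + 5 + 3 + 1 + 1 + 2 = 25
- A5: 22 + 22 + 8 + 1 + 1 + 1 = 55
- Total: 22 + 14 + 25 + 55 = 116

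Table A3 (six statins and metformin, cautions only) shares no drug with the others.

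**4. Drugs in two tables**

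| Drug | Table A1 | Other table |
|---|---|---|
| Ketoconazole | barred, 1 week off | A5: permitted, 2 days stable |
| Telithromycin | barred, 1 week off | A5: permitted, 2 days stable |
| Fluconazole | barred, 1 week off | A5: permitted, 7 days stable |
| Itraconazole | barred, 1 week off | A5: permitted, 14 days stable |
| Clarithromycin | 2 weeks = 14 days off | A4: 2 days off |
| Erythromycin | 2 weeks = 14 days off | A4: 2 days off |
| Amiodarone | 27 weeks = 27 × 7 = 189 days off | A4: 1 year, taken as 365 days off |

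All other pairs of tables share no drug. The overlap is 4 + 3 = 7, so the distinct names number 116 − 7 = 109. Pentamidine is in A4 only and is separate from these seven.

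**5. Two kinds of difference.** For the first four drugs the rules are opposed. For the last three both tables bar the drug and only the withdrawal period differs, so meeting the longer period meets both.

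**6. TMP-SMZ timing.** Sections 4.3.2 and 5.2.2 and Appendix VII give no start time for prophylaxis. Starting at least 7 days before Day 1, within screening, meets those passages and A5. Starting on Day 1 meets those passages but not A5.

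**The case against.** The strongest case is that this is loose guidance rather than a hard conflict. Appendix II is titled as guidance, and Table A4 is worded more softly than Table A1. Section 5.2.2 limits QT-prolonging drugs only where feasible. Pentamidine is conditional on TMP/SMZ being unsuitable and is one of three second-line options. Dapsone and atovaquone are unrestricted, so nothing forces a site to depart from A4. Sites may also follow institutional guidelines instead of Table 17. Exclusion criterion 7 applies when treatment starts, so it does not govern prophylaxis begun later.

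These points limit the consequence but leave the contradiction in place. None of these texts says whether A4 or Table 17 governs when a site considers pentamidine.

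For the four A1/A5 drugs, the A5 lead-in contains a *notwithstanding* clause about other exclusions and restrictions. Read literally, it lets A5 override A1. If it was meant as *subject to*, A1 governs and the conflict disappears. Because the two readings lead to opposite actions, and the A5 column heading points against its own lead-in, the clause does not settle the matter. Appendix II does invite queries to the sponsor about CYP3A4/5 agents, which gives sites a route to an answer but not a written rule.

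It stands that the three drugs with differing withdrawal periods are not contradictory, and that the TMP-SMZ point concerns timing and cross-referencing. Both are secondary.

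**Conclusion.** The concern holds. One of the four Table 17 agents, pentamidine, is also on the list of drugs not to be combined with AZD4205, and no text reconciles the two. Seven other drugs carry differing rules between Appendix II tables: four are barred in one and permitted in another, and three differ in withdrawal period only.

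This is an internal inconsistency in safety guidance that should be fixed. The documents do not allow an estimate of how many patients are affected, and for pentamidine the number may be zero. The QTcF eligibility limit, scheduled ECGs and QTcF discontinuation rules remain in place, and no endpoint analysis changes.

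The counts rest on matching printed drug names and on reading trimethoprim-sulfa in Table A5 as the TMP-SMZ of Table 17. The conclusion on pentamidine rests on the absence of any written exemption by route or for prophylaxis.

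**What to change.** Reconcile Tables A1, A4 and A5 (including the A5 column heading and its *notwithstanding* clause), exclusion criterion 7, Sections 4.3.2 and 5.2.2, and Appendix VII with Table 17:

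- Give each named prophylaxis agent, with its route, and each of the seven drugs listed twice, one consistent statement on whether and when it may be used with AZD4205.
- State which table governs when a drug appears in more than one.
- Cross-refer between Table 17 and Appendix II, including how the 7-day condition on trimethoprim-sulfa relates to the start of prophylaxis.
- Align the pulmonary monitoring part of Appendix VII, which says only that prophylaxis should be considered, with the passages that make it mandatory.
- Notify sites.

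Which rule applies to each drug is a clinical decision for the sponsor. The cost is appendix wording and a site notice, with no extra procedures or data collection.
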